4.2 Perioperative Mental Health Intervention Bundle

Our intervention bundle will be initiated prior to surgery and continue postoperatively, and will span for approximately 3 to 4 months across the perioperative period (including pre- and 3 month post-operative periods). The personalized intervention bundle is comprised of behavioral activation and medication optimization, both facilitated by specially trained interventionists on the research team.

4.2.1 Behavioral Activation

The behavioral intervention will consist of *behavioral activation* (BA), the basic premise of which is to help people with mental health problems to engage in activities that are reinforcing or meaningful and guided by their personal values [13]. The interventionists in this component of the intervention bundle, Perioperative Wellness Partners, are qualified social workers and therapists with relevant mental health experience, in addition to specific training to implement this intervention. Patients will be asked to check with their physicians if there is any question about the safety of any physical activities that are included in the behavioral activation plan. Behavioral activation as the core intervention allows for uniformity across participants from each cohort, yet enough flexibility for the actual components of behavioral activation to be individually adapted based on patient preferences. In a recent meta-analysis, behavioral activation programs improved depression and anxiety [14], as well as disability in older adults [15]. In addition, BA delivered by telehealth to older adults was cost-effective and lowered health care utilization costs over 1 year [16]. In addition to the core intervention of behavioral activation, study participants will be able to adapt the intervention by choosing activities, per their preference, with demonstrated benefit in improving depression and anxiety symptoms in older adults [17, 18]. BA will span across approximately 3 months postoperatively and will begin pre-operatively, with sessions approximately weekly or biweekly, depending on patient preference and health condition. For example, participants with hospital stays >1 week, behavioral intervention may continue weekly in the hospital setting, if the patient chooses. Finally, after discharge during the postoperative period, the behavioral intervention will continue for the remaining months/sessions. The timing, format and frequency of the behavioral activation sessions will be adapted and tailored based on patient preferences and needs. The behavioral activation process will be guided by the internal study team manual,(Appendix F) which will be adapted and calibrated as needed throughout this feasibility study, along with the adaptations to the BA patient worksheets (see Appendix H) which the patient and perioperative wellness partners may use to guide these intervention sessions and activities. We will track all adaptations to BA conduct and content during this study for our future intervention study.

4.2.2 Medication Optimization

Medications will be *reviewed and optimized*, as appropriate, by our team of interventionists including a psychiatrist, pharmacologist, perioperative wellness partners, and pharmacists. In several clinical trials including thousands of older adults, we have developed and refined a process for this review and medication optimization, including adjusting suboptimal dosing for anti-depressants and discontinuing medications that are harmful for brain health (such as anticholinergics [19]). Medication optimization consists of a simple set of principles: reconcile patient's medications, identify the patient's likely need for, and interest in, a medication adjustment, make the adjustment, and assess the response to that adjustment. Benzodiazepines, non-benzodiazepine sedatives, strong centrally acting anticholinergics, and antihistamines may be deprescribed as they increase the risk for falls and delirium. We will follow the principles of shared decision-making with patients for medication changes, identifying DEMS (deprescribing eligible medications) which worsen functional recovery, impair cognitive function, and increase medical risks like falls, delirium, and bleeding. With the patients' consent, we will initiate communication with the prescribing provider regarding any changes to medications (DEMs in particular) which they have prescribed. While the participant is in-hospital, the interventionist's role will include coordinating with the hospital team to ensure that medication changes that were introduced preoperatively are maintained in-house and that no new inappropriate medications are initiated. We will give voice to patient and family concerns by helping

them communicate with the hospital (and subsequent transitional) provider team. After discharge, and up to approximately 3 months postoperatively, the interventionist will ensure that medication changes are reconciled during transitions of care. The interventionists will ensure the agreed-upon changes are implemented, or an alternative course of action is justified. The internal study team manual for medication optimization will be updated as needed in the feasibility study. Please see Medication Optimization SOP in Appendix F.

4.3 Evaluation Measures and Outcomes

Preoperative assessments along with preoperative and postoperative surveys (assessments described in 4.1 above) regarding quality of life, depression, and anxiety will be obtained from all study participants. Study participants will be followed for approximately 3 months after their scheduled procedure. They will complete follow-up surveys at approximately 1 month and approximately 3 months after surgery by either web-based survey, mail, or via a telephone interview (or in person if the visit coincides with a clinic visit). Collection of falls data will occur approximately monthly for 3 months by phone with study coordinator, or REDCap, or in person. The results of follow-up surveys will be obtained via secure REDCap e-mail link, mail, or telephone survey. Rehospitalizations will be obtained from patient self-report and/or EHR at the end of study follow-up. Please see Table 2.1 for list of outcomes and details.

Additional pre-operative data related to patient medical, social and surgical history, problems, diagnosis and medication lists will be retrieved from the patient electronic health record using the research data core (RDC). Post-operative data including post-operative acute diagnoses (e.g., complications), additional procedures, postoperative opioid use, pain scores will also be retrieved.

4.3.1 Primary Feasibility Outcomes

Reach of the study: patients who agreed to participate in the study out of total eligible to participate. Reach of the intervention bundle: patients who completed the interventions out of patients who agreed to participate in the pilot.

4.3.2 Secondary Feasibility Outcomes

Completeness of planned RCT primary outcome data collection at specified timepoints

4.3.2.1 Potential Study Primary Outcomes for Planned RCT

Effectiveness outcomes will include the primary outcome measure of PHQ-ADS, a validated composite scale of depression and anxiety symptoms [7] measured at baseline, 1, and 3 months after surgery. The Behavioral Activation for Depression Scale, or BADS (activation subscale), is our primary measure of target engagement. BADS is a sensitive and pragmatic assessment of the mechanism of change in Behavioral Activation. Approximately three months post-operative is the primary endpoint.

4.3.2.2 Potential Study Secondary Outcomes for Planned RCT

The secondary outcomes will include QoL measured via the VR-12 Health Survey, and other perioperative outcomes of interest, nominated by our stakeholders as key outcomes of interest, including:

1. In-hospital: (i) Delirium incidence, assessed by trained research coordinators using the Ultra Brief and 3-D Confusion Assessment Method, [20] as in our prior work [19], and/or Delirium incidence may be assessed by EHR review using the CHART-DEL [23] method ; (ii) Length of Stay (hospital and ICU), assessed by EHR review.
2. Post-discharge: (i) Falls, prospectively assessed monthly falls reported by patients. (ii) All-cause rehospitalization out to approximately 3 months postoperative, assessed from EHR report, supplemented by review with patient and caregiver.
3. Process outcomes: Shared Decision Making (modified collaboRATE) 3 item survey will be administered at post-end of study. CAHPS modified survey will be administered after the intervention is complete, as part of post-end of study surveys.
4. Implementation-potential surveys: Acceptability of Intervention Measure, Intervention Appropriateness Measure, Feasibility of Intervention Measure.

4.3.3 Exploratory Feasibility Outcomes

Implementation potential

Completeness of planned RCT primary outcome data collection at specified timepoints

Table 2. Feasibility study outcomes and potential study primary and secondary outcomes for planned RCT. Note: The surveys and questionnaires will be administered via email or research coordinators over the telephone.

Outcomes	Specific measure: description	Source	Timepoint
Reach (Primary)	Reach of the study: patients who agreed to participate in the study out of total eligible to participate Reach of the intervention bundle: patients who completed the interventions out of patients who agreed to participate in the pilot	Electronic Health Record, Research data warehouse	End of Study
Completeness of planned RCT primary outcome data collection at specified timepoints (Secondary)	Defined as a percentage of instrument or data fields completed for- Patient Health Questionnaire Anxiety and Depression Scale (PHQ-ADS) ⁶² : 16-item scale with components of the Patient Health Questionnaire-9 and Generalized Anxiety Disorder Scale (collected at baseline; 1 mo; 3 mo)	Research data warehouse	End of Study
Implementation-Potential (Exploratory)	Acceptability, appropriateness and feasibility of the interventions: The Acceptability of Intervention Measure (AIM), the Intervention Appropriateness Measure (IAM), and the Feasibility of Intervention Measure (FIM). ⁷⁷ Each survey has 4 items in a Likert scale ranging from completely disagree to completely agree.	Surveys	End of Study

Completeness of planned RCT secondary outcomes data collection at specified timepoints (Exploratory)	
We will be measuring the completeness of data collection for the following potential secondary outcomes for the planned RCT secondary outcomes:
 
 • Quality of Life (collected at baseline; 1 mo; 3 mo) • In-hospital delirium incidence (collected at baseline; in-hospital/postoperatively) • Post-discharge falls (collected at baseline; 1 mo; 2 mo; 3 mo) • Medication optimized and adherence to medications (collected at baseline; 1 mo; 3 mo) • Length of stay (both hospital and ICU) • All-cause rehospitalization (collected in the hospital/postoperatively; 1 mo; 3 mo) • Persistent postsurgical pain (collected at 1 mo; 3 mo) • Patient experience (collected at end of study) • Shared decision making (collected at end of study) 	Research data warehouse	End of Study
---	---	-------------------------	--------------

Table 2.1 Details on Potential Study Outcomes for Planned RCT

Effectiveness Outcomes		Data Source	Description	Data Collection Mechanism	Time points (Baseline, 1, 2, 3 month-post-op or EOS)
Primary (Clinical)	Anxiety and Depression	Patient Health Questionnaire Anxiety and Depression Scale (PHQ-ADS)	A validated composite of symptoms of depression and anxiety	Patient Self-Report	Baseline; 1 mo and 3 mo
Primary (Target Engagement measure)	Anxiety and Depression / Target Engagement	Behavioral Activation for Depression Scale (BADS)	A validated scale utilized to measure target engagement in studies of geriatric depression	Patient Self-Report	Baseline; 1mo; 2mo; 3mo
Secondary (Clinical)	Quality of Life	The Veterans RAND 12 Item Health Survey (VR-12) ⁴³	A patient-reported global health measure. The questions in this survey correspond to the QOL domains of general health	Patient Self-Report	Baseline; 1 mo and 3 mo

			perceptions, physical functioning, role limitations due to physical and emotional problems, bodily pain, energy/fatigue levels, social functioning and mental health.		
	In-hospital delirium incidence	Ultra Brief CAM to screen for 3D CAM, and if UBCAB positive, then 3D CAM Confusion Assessment Method ⁴⁴	UB-CAM and 3D CAM are standardized, evidence-based interview that enables researchers and clinicians, following structured training, to reliably and reproducibly identify the four cardinal features of delirium.	UB-CAM and 3D CAM Research Coordinator-Administered	Baseline/pre-op; In-hospital: During post-op hospital stay; up to twice daily for 3 days; if not in person, UB-CAM may be collected by phone.
	Family Confusion Assessment Method	FAM-CAM	The FAM-CAM is intended to evaluate for evidence of delirium based on observations from family members or caregivers. The instrument facilitate and educate caregivers to pick up acute changes in mental status, and the earliest signs of cognitive changes in frail or cognitively impaired older persons.	Survey or phone	Baseline/pre-op; post-op, once every week for 4 weeks.
	Post-discharge falls	Patient Reported Falls	A Patient Reported Falls survey will be collected monthly either by phone or REDCap link, at follow-up clinic appointments.	Patient Self-Report	Baseline; 1mo; 2mo; 3mo
	Medication list	Data collection Appendix D; Appendix G	Review of all patient medications, confirming accuracy of EHR med list, number of medications optimized and medication adherence	Patient Self-Report/ study team member verifies EHR meds list with patient	Baseline, initial intervention visit; approximately 1mo; approximately 3mo at end of

					intervention.
	Length of stay (both hospital and ICU)	Research Data Core	Standardized reports on the research data core (RDC) warehouse will generate statistics of enrolled patients regarding the length of stay, rehospitalization, and related clinical metrics.	EHR report	In-hospital: at ICU and hospital discharge
	All-cause rehospitalization	Research Data Core		EHR report	Post-op: 1 mo and 3 mo
Secondary (Process)	Patient experience	Modified-Consumer Assessment of Healthcare Providers and Systems (CAHPS) ⁴⁵	The modified CAHPS asks patients about their experience before surgery, during surgery, and after surgery.	Patient Self-Report	Post-EOS
	Shared decision making	Shared decision making process CollaboRAT E modified	A 3-item survey modified to measure shared decision making, following encounters with study interventionists and perioperative wellness partners	Patient Self-Report	Post-EOS
Implementation Outcomes		Data Source	Description	Data Collection Mechanism	Time points
	Implementation-Potential (I)	Acceptability of Intervention Measure, Intervention Appropriateness Measure, Feasibility of Intervention Measure	Acceptability, Feasibility and Appropriateness 4-item Likert scale survey	Patient Self-Report	Post-EOS

In addition to these outcomes, we will also be assessing fidelity of our intervention bundle which will assess the extent to which an intervention bundle is carried out by our perioperative wellness partner, as intended and consistently across different settings, and patients. To track this, we will observe and take notes on the patient and the perioperative wellness partner during the behavioral intervention and medication optimization sessions with the patient and clinician. Observations will involve a member of the research team observing the wellness partner over a period of time or number of intervention sessions. We will capture data on patient interactions with the wellness partner, their delivery of the intervention bundle, any observed barriers and facilitators to the intervention adherence, acceptance and fit within the perioperative workflow. These observation sessions of patients and their wellness

partners will be selected based on a convenience sample. If the patient agrees to audio/video recording, the intervention sessions will be audio recorded (or audio/video if the patient prefers to meet by Zoom teleconference). The observations may be made by a member of the research team reviewing the recorded sessions.

Lastly, we will also obtain various stakeholder perspectives on the intervention bundle after the intervention period has been completed using semi-structured interviews. We will conduct interviews with patients, and caregivers, and the topics of discussions will be guided by an implementation science framework referred to as CFIR (Consolidated Framework of Implementation Research). The interviews will explore the participants' perceptions, attitudes, experiences with the intervention bundle, intervention bundle acceptability and detailed accounts of participants' experiences after the intervention has been stopped with regards to intervention sustainability and maintenance. These insights will inform whether the intervention bundle needs to be changed or adapted before our future trials (see interview guides in Appendix J). Interviews will be conducted via Zoom or telephone and will be digitally recorded and transcribed verbatim.

5 Data Analysis

The quantitative data will be used to provide baseline and post-intervention comparisons on a number of outcome variables relevant to the intervention, with the hypothesis that performance on these measures will improve post intervention. These data will also be used to estimate effect sizes for further trials so that these are suitably powered. Quantitative data will be tabulated for descriptive purposes. Given the small sample size, a non-parametric approach will be used to calculate effect size data ($r = Z/\sqrt{N}$), where Z is the standardized test-statistic from a Wilcoxon signed-rank test and N is the sample size, along with the associated 95% confidence interval. The r values will be calculated for the timepoint as compared to baseline.

The observation data will be analyzed using open coding and FRAME analytic framework that helps track any adaptations to intervention bundle and delivery. The interview data will be analyzed using thematic analysis [8].

Table 3. Study Calendar

	Time 0	Baseline/ Time 1	In- Hospital / Post-Op	1 mo follow up	2 mo follow up	3 mo follow up	Post- EOS
Patient Consent	X						
Patient Screening (Appendix A)	X						
Patient Baseline surveys (Appendix D)		X					
Caregiver Consent		X					X
Patient Delirium Assessment (Appendix K) pt UB/ 3-D CAM ; & Caregiver if applicable, FAM-CAM		X (pt)	X(pt) twice daily x 3	FAM- CAM if applicable			

1x weekly for 4 weeks.			days post-op	(weekly x 4wks)			
Patient Follow-up 1 & 3 mo Surveys (Appendix G)				X		X	
Patient Monthly Surveys (Appendix L)				X	X	X	
Patient Post-EOS Surveys (Appendix I)							X*
Patient Semi-Structured Interview (Appendix J)							X*
Caregiver Semi-Structured Interview (Appendix J)							X*
Behavioral Activation and Medication Review Intervention Sessions				Approximately 6-12 sessions as needed (per Pt preference) from Baseline, continuing for up to approximately 3 months post-op during study data collection, until EOS.			

*Post-End of Study (EOS) implementation surveys and semi-structured interviews will be completed approximately 2 weeks after EOS assessment.

6 Patient Participant Retention

Participant retention strategies will include flexibility in scheduling follow-up visits and coordination of research (both data collection and intervention) visits with the clinical visits. Remuneration for each data collection study visit will be provided after the final follow-up visit to encourage retention as well. For patients who are difficult to reach by phone, we may utilize a reminder, the *Attempting to Reach You Letter* (Appendix N) to remind them to contact either the Perioperative Wellness Partner or the Study Coordinator for a study session.

7 Protection of Human Subjects

The study will be conducted under appropriate Washington University Institutional Review Board guidance, and use only IRB-approved study procedures and instruments. The study team will follow the protocol under the supervision of the PI, a mentor with several years of experience in the conduct of human volunteer studies, and co-Investigators with extensive expertise in human subject research. All members of the study team are IRB-approved and trained in Good Clinical Practice and Human Subjects Research education.

8 Data Management for Participant Privacy

A unique patient number (UPN) will be assigned at enrollment and used wherever possible on the case report forms (CRF) to identify data, minimizing use of patients' names or personal identifiers in data.

All paper data will be stored under lock and key (two locked doors, e.g., office, file cabinet) and all electronic data will be hosted on a password-protected, firewall-secured server that is only accessible to the research team through password-protected departmental computers. Surveys that are completed electronically will be administered via the Research Electronic Data Capture (REDCap) server. All REDCap email correspondence will be sent using secure survey links. Similarly, interview data from caregivers will follow the same security and storage policies.

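### Do the mismatched labels for the completeness outcomes in 4.3.2, 4.3.3, Table 2 and Table 2.1 leave the secondary feasibility outcome undefined?

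*Combined protocol and SAP*

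**What the plan says.** Section 4.3.2 names one secondary feasibility outcome: "Completeness of planned RCT primary outcome data collection at specified timepoints". Table 2 gives it the same rank and defines it: "Defined as a percentage of instrument or data fields completed for- Patient Health Questionnaire Anxiety and Depression Scale (PHQ-ADS"), at baseline, 1 month and 3 months.

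Section 4.3.3, on exploratory feasibility outcomes, lists implementation potential and then the 4.3.2 line again, word for word. Table 2 has a different second exploratory entry: "Completeness of planned RCT secondary outcomes data collection at specified timepoints". One item under that entry is "Persistent postsurgical pain (collected at 1 mo; 3 mo").

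Section 4.3 sends the reader to the other table: "Please see Table 2.1 for list of outcomes and details". Table 2.1 labels PHQ-ADS as the clinical primary and BADS as "Primary (Target Engagement measure"), the latter at baseline, 1, 2 and 3 months. Section 4.3.2.1 says that "BADS (activation subscale), is our primary measure of target engagement". Table 2.1 has no row for pain. Section 4.3 says of the record review that "postoperative opioid use, pain scores will also be retrieved", and section 4.1 lists a brief pain survey at baseline.

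**The concern.** Read literally, the only secondary feasibility outcome has two ranks. It also seems to have two possible contents, since Table 2.1 and the plural heading of 4.3.2.1 place BADS beside PHQ-ADS among the primary outcomes while Table 2 counts PHQ-ADS alone. Pain is the reverse case: its completeness is to be reported, but the table of outcome details gives it no instrument or source.

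Feasibility of the outcome measures is part of the first objective, and the pilot is meant to inform three later trials. If rank and content were truly open, someone could decide after seeing the data which completeness figures count as pre-specified. A poor figure could then be played down as exploratory or a favourable instrument added.

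**Working it through.** The plan states no figure for this outcome, so the check is mainly a comparison of texts.

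**Rank.**

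| Place | Completeness of RCT primary outcome | Completeness of RCT secondary outcomes |
|---|---|---|
| 4.3.2 | secondary | not mentioned |
| Table 2 | secondary | exploratory |
| 4.3.3 | exploratory | not mentioned |

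Two of three places agree on the first column. The line in 4.3.3 differs from Table 2's exploratory entry in essentially one word (primary for secondary). Putting that word right makes all three places agree and supplies the entry missing from 4.3.3. No other reading does both.

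**BADS.** Table 2 states a definition, and it names PHQ-ADS only. The row title refers to a single primary outcome, whereas the exploratory row uses the plural. Section 4.3.2.1 describes PHQ-ADS as the primary outcome measure and BADS as a measure of the mechanism of change. Table 2.1 keeps the clinical primary apart from the target-engagement primary. The plural heading of 4.3.2.1 points the other way, but a heading does not override an express definition. Table 2.1 gives details of outcomes for the future RCT; it does not define the pilot's feasibility outcome.

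**Pain.** Table 2 places it at 1 and 3 months. Those are the visits at which the study calendar (Table 3) schedules the Appendix G follow-up surveys. Appendix G is not among the documents, so the instrument cannot be shown to be missing. Absence from 4.3.2.2 is weak evidence, because that list is introduced as a set of examples. Medication optimization and adherence, for instance, is in both tables but not in 4.3.2.2.

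**Does a number move?** Inputs: at most 45 patients (section 3); PHQ-ADS at 3 timepoints (Table 2); BADS at 4 timepoints (Table 2.1). Scheduled forms = patients × timepoints.

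- PHQ-ADS alone: 45 × 3 = 135.
- BADS: 45 × 4 = 180.
- Both: 135 + 180 = 315, of which BADS would be 180/315 = 57.1%.

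The contrast of 135 with 315 matters only if the two instruments are pooled into one denominator. The documents nowhere describe such pooling. Reported by instrument and timepoint, the PHQ-ADS percentage at 3 months has a denominator of at most 45 whether or not a BADS row is printed beneath it. Correcting the rank in 4.3.3 changes no percentage.

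**Does a decision move?** Section 5 tabulates the quantitative data descriptively and computes effect sizes against baseline. It sets no test, margin or target for completeness, and no go/no-go rule for the later trials uses it.

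**The case for a change.** The strongest case for a change is that calling something a probable slip explains it without correcting it. No sentence says whether text or table governs. BADS is called a primary measure yet falls in neither completeness row. The wording on instrument or data fields allows two different percentages and gives no denominator. The repair would cost a few words and no new data, and the outcome is the only one at its rank.

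Part of this stands. The mismatches are plain in the current text, and a sponsor revising the document anyway could align 4.3.3 with Table 2 and add a pain cross-reference. Whether BADS completeness will also be shown is a fair question to ask. FAM-CAM, which has a row in Table 2.1 but is not named in Table 2, belongs to the same class.

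The rest does not carry. Reporting BADS completeness as an extra descriptive row needs no permission from Table 2 and displaces nothing. The choice between whole instruments and fields is one an analyst can settle by showing both. Stricter rules, such as requiring every item to be answered or keeping deaths and withdrawals in the denominator, are debatable preferences. They would fill in detail and would not correct a wrong rule.

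**Conclusion.** No change to the plan is needed. The rank in 4.3.3 is a clerical slip resolved by 4.3.2 and Table 2. The BADS point is not a contradiction, because Table 2 defines the outcome by PHQ-ADS and 4.3.2.1 is consistent with that. The pain entry is a missing cross-reference. The effect on any stated figure, error rate or decision is nil: the outcome is descriptive, with at most 45 patients at any timepoint.

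This rests on two assumptions: that completeness is reported separately by instrument and timepoint, as the timepoints in Table 2 suggest, and that no progression rule using it exists outside the documents. If a later trial's go/no-go decision were tied to a completeness threshold, the rank, content and denominator would have to be fixed beforehand. The documents set no such threshold.

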The study will address the following objectives: (1) demonstrate the feasibility of our study procedures including patient recruitment, screening and outcome measures, and feasibility of adapting our intervention bundle and its intervention delivery process within three older surgical patient populations (i.e., orthopedic, oncologic, and cardiac); (2) empirically test the effectiveness of our adapted perioperative mental health intervention bundle with clinically significant symptoms of depression and/or anxiety; and lastly (3) identify implementation strategies to ensure acceptability, feasibility, and adoption of our intervention bundle by patient and clinician stakeholders. Insights gained from this pilot study will inform the design of three clinical trials that are planned to start in Jan 2023. This project is led by research team members of the newly established Center for Perioperative Mental Health <https://perioperativewellness.wustl.edu/> that strives to improve perioperative mental health and well-being for older adults.

3 Study Setting and Participants

The study will be conducted at Barnes-Jewish Hospital and Washington University School of Medicine locations, including Siteman Cancer Center and Barnes-Jewish West County Hospital. Participants will include patients and caregivers. We expect to recruit and enroll up to 70 participants total in this study: up to 45 patients, up to 12-15 in each of 3 surgical cohorts; up to 25 caregiver participants.

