3.4.2 Caregiver consent

Caregivers will be invited to participate in semi-structured interviews about the intervention bundle that can be conducted via Zoom/Phone or in-person depending on participant convenience and choice. Hence, they will be consented verbally or with a written consent depending on their participation. If they consent to a semi-structured interview (Appendix J). The interviews with study patient caregivers, will provide valuable feedback on the intervention bundle. Caregivers may also consent verbally to participate in the FAM-CAM confusion and delirium assessment via phone, mail, or email link to REDCap survey.

4 Study Design

This is a feasibility study utilizing mixed methods. All eligible and consenting patients will receive the intervention bundle and will undergo a standard battery of assessments prior to the intervention and will be followed for approximately 3 months in the postoperative period. In conjunction with the

quantitative data collected, qualitative methods will be employed to evaluate acceptability, implementation and practicality of the intervention.

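### Section 5 wants pilot effect sizes to power later trials, but its only effect size is a single-arm pre/post r, which cannot supply a between-arm effect

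*Combined protocol and SAP*

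**What the plan says.** Section 5 (Data Analysis) gives the quantitative data two uses. One is a comparison of baseline with post-intervention values, "with the hypothesis that performance on these measures will improve post intervention". The other concerns later trials: "These data will also be used to estimate effect sizes for further trials so that these are suitably powered". The effect size is r = Z/√N, with Z from a Wilcoxon signed-rank test and a 95% CI. Its contrast is within patient: "The r values will be calculated for the timepoint as compared to baseline".

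Section 4 (Study Design) has one arm: "All eligible and consenting patients will receive the intervention bundle". The opening statement of objectives says "Insights gained from this pilot study will inform the design of three clinical trials that are planned to start in Jan 2023", and Objective 2 is to "empirically test the effectiveness of our adapted perioperative mental health intervention bundle".

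Section 4.3.2.1, on potential primary outcomes for the planned RCT, says "Effectiveness outcomes will include the primary outcome measure of PHQ-ADS" and "Approximately three months post-operative is the primary endpoint". Section 3.1.1 requires a PHQ-ADS score of at least 10 for entry. Section 3.3.2 puts a PHQ-4 pre-screen of at least 3 before it. Section 4.1 lists PHQ-ADS among the baseline assessments as the value taken at screening.

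No section gives a control-arm course, an external control, a between-arm difference, or a rule for turning r into one.

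**The concern.** An RCT is powered on a difference between arms. A pre/post r in treated patients mixes any effect of the bundle with surgical recovery, usual care and the way patients were selected. Section 5 assigns these effect sizes a powering role without saying how the mixture would be separated.

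For PHQ-ADS, selection adds a known artefact. Patients enter because their score was high on one occasion, and that same score is the starting point for measuring change. Some fall is expected without any treatment. Surgery may push the other way if symptoms worsen without the bundle.

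Two things are at stake. The planned trials could be sized on a number that does not measure what they will test. And because improvement is the stated hypothesis, a positive r could be read as meeting Objective 2.

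**Working it through.** The documents state no power, significance level, SD, effect size or sample-size calculation, so there is no figure to reproduce. The check is one structural step and two illustrations.

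**1. What r contains.** Let τ be the bundle's effect on the mean fall in score, and U the mean fall the same patients would have shown without it.

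- Pilot: observed fall = τ + U.
- RCT: (τ + U) − U = τ.

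The pilot observes only the sum, and nothing in the documents supplies U. This step needs no numerical assumption and applies to every outcome analysed this way.

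**2. Regression to the mean alone (PHQ-ADS).** Positive r means improvement.

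- From the documents: entry at 10 or more (Section 3.1.1), screening score used as baseline (Section 4.1), up to 45 patients (Section 3), 16 items (Table 2).
- Assumed: mean 8, 10 or 12 and SD 7, 8 or 9 in the screened population; correlation ρ before selection of 0.5, 0.6, 0.7 or 0.8; normal scores rounded to integers and bounded at 0 to 48; τ = 0; no drift over time. The PHQ-4 pre-screen is not modelled.

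Expected fall = (1 − ρ) · SD · φ(c) / (1 − Φ(c)), with c = (9.5 − mean)/SD.

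Example with mean 10, SD 8, ρ = 0.7: c = −0.0625, and φ/(1 − Φ) = 0.398/0.525 = 0.758. The fall is 0.3 × 8 × 0.758 = 1.82 points.

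Over the 36 combinations the formula gives 0.82 points (mean 12, SD 7, ρ = 0.8) to 4.08 points (mean 8, SD 9, ρ = 0.5; 3.84 when scores are bounded). Simulated signed-rank results at n = 45:

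| Extreme of the grid | Average r | Share with Z > 1.96 |
|---|---|---|
| Mean 12, SD 7, ρ = 0.8 | 0.19 | 24% |
| Mean 8, SD 7, ρ = 0.5 | 0.46 | 91% |

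The 1.96 line is a yardstick chosen here. The plan sets no such rule.

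**3. The opposite direction.** Mean 10, SD 8, τ = 0, with an assumed untreated worsening of 4 points:

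| ρ | Fall from selection | Net change (fall − 4) | Average r |
|---|---|---|---|
| 0.5 | 3.03 | −0.97 | −0.13 |
| 0.6 | 2.43 | −1.57 | −0.23 |
| 0.7 | 1.82 | −2.18 | −0.34 |
| 0.8 | 1.21 | −2.79 | −0.50 |

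A worsening about equal to the second column brings r to about zero. A bundle with no effect can therefore give a clearly positive or a clearly negative r, depending on quantities that the documents do not give.

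**The case against.** **It is a feasibility study.** Section 4 says so, and the declared outcomes are reach, completeness and implementation potential. This stands: those outcomes are untouched. It does not answer the sentence that gives the effect sizes a powering role, nor Objective 2.

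**Section 5 never says r will be taken as the between-arm difference.** This also stands. A reader might infer that the later trials are, or will be, wrongly sized. The documents do not support that, because the sizing of those trials is not in them. What they show is a stated powering aim with no route from r to the quantity needed.

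**A reader might infer that r is biased upwards.** Regression to the mean does raise r for PHQ-ADS, but the untreated course after surgery is unknown, so the net direction is unknown too. The selection argument is made only for PHQ-ADS, the scale on which patients are selected.

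**A reader might convert r into a range of wrong sample sizes.** The documents do not support a range, because they do not give the RCT's analysis. Take r = 0.40, which corresponds to a mean change of 0.435 SDs of change, and suppose all of it is treatment effect. At correlations 0.3, 0.5, 0.7 and 0.8, with 80% power and two-sided 5%:

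- unadjusted follow-up scores: 60, 83, 139 and 208 per arm;
- change scores: 83 per arm throughout;
- baseline-adjusted analysis: 54, 63, 71 and 75 per arm.

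The wide spread belongs to the first analysis only. It also assumes equal SDs at both times, which fails after selection: with mean 10, SD 8 and ρ = 0.7, enrolled patients have SDs of about 4.9 at baseline and 6.6 at follow-up. No per-arm figure is claimed here.

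**The means and SDs come from no section of the documents.** Correct. They are assumptions, and the structural point does not depend on them.

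**Conclusion.** The point holds and should be fixed. The use that Section 5 states for its effect sizes cannot be delivered by the one effect size it defines, because a single-arm pre/post r contains no control-arm change and no other section supplies one. This rests on the text alone.

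The size of the distortion for PHQ-ADS is illustrative. It rests on the assumed population mean, SD and correlation, on approximate normality, on n = 45, and on leaving out the PHQ-4 pre-screen. Within that frame the ranges in the two tables show that r can look favourable or unfavourable with no treatment effect.

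Objective 2 falls with the same argument: a pre/post comparison in one arm can describe change but cannot test effectiveness.

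**What to change.** In Section 5, replace the powering sentence with wording such as:

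> Pre/post r values are descriptive of within-patient change and will not be used as the between-arm effect size for planned RCTs. To inform their design, the pilot will report the 3-month PHQ-ADS SD, the baseline to 3-month correlation (both in enrolled patients) and retention, each with a 95% CI.

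In the statement of objectives, reword Objective 2 as describing change in symptoms. The pilot protocol need not commit the later trials to a particular sizing basis.

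The cost is wording plus summaries of data already collected, with no new patients, visits or questionnaires. The objective becomes less ambitious, and the planning inputs will be imprecise. By normal theory, the 95% CI for the SD runs from about 0.83 to 1.26 times the estimate at n = 45, and from 0.81 to 1.30 times if 36 patients are followed (an assumed figure). An observed correlation of 0.7 at n = 45 has a Fisher-z 95% CI of about 0.51 to 0.82.
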